During the first 8 days in the inpatient unit (Day 57 to Day 64) following challenge, subjects will be monitored daily for AEs, gastrointestinal or other systemic signs and symptoms. Subjects will be assessed for vital signs (including sitting blood pressure, temperature and pulse rate) according to local standards for inpatient care. Stool analysis will be carried out daily during the inpatient stay. All stools will be collected and visually assessed for consistency, blood or mucus. Stools that are loose or watery (grades 3-5) will be weighed, and if there is visible blood, a Hemoccult test will be performed to confirm presence of occult blood. Up to two stools with blood present by visual inspection in a 24 hour period will be tested by Hemoccult. Study staff will record the information in the subject's source document. If a subject is unable to produce a stool by midnight, a rectal swab will be obtained (up to 2 adequately collected swabs per day). Study staff will record the information in the subject's source document. The first stool sample collected during a 24 hour period on the day after challenge agent administration (from 00:01 to 24:00) will be analyzed by culture and quantitative polymerase chain reaction (qPCR) specific for S. sonnei 53G. The day before discharge (Day 64), two stool samples will be collected to confirm that the subject is no longer shedding. Instructions for appropriate

205626 (S SONNEI MONO GMMA SBVGH-003 [H03_03TP])
Protocol Amendment 6 Final

collection, transportation and storage of stool samples will be provided to the investigators. For diarrhea episodes to be considered as separate episodes, there should be at least a 6-hour interval between them (refer to Section 4 for details on stool grading).

On the 5th day after challenge (Day 62), subjects will receive as first-line treatment 500 mg of ciprofloxacin twice daily for 3 days. Subjects with contraindication to ciprofloxacin may receive as second-line treatment trimethoprim-sulfamethoxazole (160 mg/800 mg twice daily), amoxicillin (500 mg three times daily) for 5 days, or any antibiotic that is deemed suitable according to local guidelines and the investigator's assessment can be used.

Subjects may be treated with antibiotics before the 5th day after challenge (Day 62) if:

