4.2. Dysentery (Amended: 23 July 2019)

For the purpose of the endpoint "Rate of shigellosis as defined by the CHIM expert working group occurring within a period starting with challenge visit and lasting until the end of the inpatient stay, in all subjects", dysentery is defined as follows:

• At least 2 loose stools with gross blood (hemoccult positive) in 24 hours AND [oral temperature ≥38.0°C OR ≥1 moderate constitutional/enteric symptom OR ≥2 episodes of vomiting in 24 hours]. In this case constitutional/enteric symptom are the following: nausea, abdominal pain, abdominal cramping, myalgia, arthralgia, malaise.

For the purpose of the endpoint "Rate of shigellosis, as defined by: severe diarrhea OR moderate diarrhea with fever or with one or more moderate constitutional/enteric symptoms OR dysentery", dysentery is defined as follows:

• At least 2 loose stools with gross blood (hemoccult positive) in 24 hours AND [≥1 reportable constitutional/enteric symptom]. In this case constitutional/enteric symptom are the following: headache, fatigue, arthralgia, malaise, myalgia, chills, nausea, abdominal cramping, abdominal pain, gas, anorexia, vomiting.

For the purpose of the endpoint "Rate of more severe shigellosis as defined by: severe or moderate diarrhea with fever or with one or more severe constitutional/enteric symptom OR dysentery [[≥ 2 loose stools with gross blood (hemoccult positive) in 24 hours] AND [oral temperature $\geq 38.0^{\circ}C$ $OR \geq 1$ severe constitutional/enteric symptom]].", dysentery is defined as follows:

• At least 2 loose stools with gross blood (hemoccult positive) in 24 hours] AND [oral temperature ≥38.0°C OR ≥1 severe constitutional/enteric symptom]. In this case constitutional/enteric symptom are the following: headache, fatigue, arthralgia, malaise, myalgia, chills, nausea, abdominal cramping, abdominal pain, gas, anorexia, vomiting.

For the purpose of the endpoints "Dysentery" and "Confirmed S. sonnei 53G shedding AND moderate or severe diarrhea OR dysentery OR presence of oral temperature ≥ 38.5°C OR presence of one or more severe intestinal symptoms (abdominal pain, cramping, nausea, vomiting, gas, and anorexia)", dysentery is defined as follows:

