• A Grade 3, 4, or 5 stool with gross blood on at least 2 occasions within 24 hours and presence of constitutional/enteric symptoms. In this case, constitutional/enteric symptoms consist of headache, fatigue, arthralgia, malaise, myalgia, chills, nausea, abdominal cramping, abdominal pain, gas, anorexia, vomiting, and fever.

(Amended: 23 July 2019)

205626 (S SONNEI MONO GMMA SBVGH-003 [H03_03TP])
Protocol Amendment 6 Final

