4.3. Shigellosis

For the primary and secondary objectives in the challenge phase of the study, the protocol primary case definition for shigellosis is:

• Shedding of *S. sonnei* 53G accompanied by moderate or severe diarrhea OR shedding with an oral temperature of ≥ 38.5 °C).

For the secondary objectives in the challenge phase of the study, 2 definitions of shigellosis are used:

- 1. CHIM working group case definition for shigellosis as defined by any one of the three following possible endpoints:
 - Severe diarrhea defined as [≥6 loose stools in 24 hours] OR [>800 grams loose stools in 24 hours]
 - Moderate diarrhea defined as [4-5 loose stools in 24 hours OR 400-800 grams loose stools in 24 hours] AND [oral temperature ≥38.0°C OR ≥1 moderate constitutional/enteric symptom OR ≥2 episodes of vomiting in 24 hours]
 - Dysentery defined as [≥2 loose stools with gross blood (hemoccult positive) in 24 hours] AND [oral temperature ≥38.0°C OR ≥1 moderate constitutional/enteric symptom OR ≥2 episodes of vomiting in 24 hours].
- 2. Shigellosis as defined by any one of the three following possible endpoints:
 - Severe diarrhea defined as [≥6 loose stools in 24 hours OR >800 grams loose stools in 24 hours]
 - Moderate diarrhea defined as [4-5 loose stools in 24 hours OR 400-800 grams loose stools in 24 hours] AND [oral temperature ≥38.0°C OR ≥1 moderate constitutional/enteric symptom].
 - Dysentery defined as [≥2 loose stools with gross blood (hemoccult positive) in 24 hours] AND [≥1 reportable constitutional/enteric symptom].

For the secondary objectives in the challenge phase of the study, more severe shigellosis is defined by any one of the two following possible endpoints:

- Moderate OR severe diarrhea [≥4 loose stools in 24 hours OR ≥400 grams loose stools in 24 hours] AND [oral temperature ≥38.0°C OR ≥1 severe constitutional/enteric symptom].
- Dysentery defined as [≥2 loose stools with gross blood (hemoccult positive) in 24 hours] AND [oral temperature ≥38.0°C OR ≥1 severe constitutional/enteric symptom]. (Amended: 23 July 2019)

205626 (S SONNEI MONO GMMA SBVGH-003 [H03_03TP])
Protocol Amendment 6 Final

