9.1.3.3. Solicited events after challenge phase

During the challenge phase after the subjects have received the challenge agent, events associated with the administration of the challenge agent will be collected and recorded by the investigator in the CRF. These events include diarrhea, abdominal pain, abdominal cramps, gas, anorexia, nausea, headache, myalgia, malaise, arthralgia, fever, and vomiting beginning the day of administration of study challenge agent until 7 days after challenge (i.e., Day 64). Any unresolved events will be followed to resolution or stabilization. Oral rehydration will be initiated and recorded for subjects with a Grade 2 or higher AE of diarrhea, vomiting, dysentery or dehydration. The hydration of subjects developing diarrhea will be maintained with oral electrolyte solutions by offering at least 1.5 mL for each gram of diarrheal stool lost, as tolerated. Subjects who develop vomiting will be offered at least 1.0 mL for each gram of emesis lost, as tolerated. Subjects will be evaluated by a physician who will consider intravenous hydration for subjects who:

- Cannot tolerate oral fluids,
- Experience fluids loss that exceeds their ability to drink replacement fluids,
- Have > 1000 mL deficit in intake in a 24 hour period,
- Experience weight loss of more than 5%,
- Have urine specific gravity > 1.030 for 12 hours,
- Have syncope or near-syncope,
- Grade 3 tachycardia, or
- Grade 3 hypotension.

If the subject is unable to tolerate fluids by mouth and intravenous fluids are deemed necessary by the assessing physician, a 0.9% sterile saline solution 1-liter bolus will be administered intravenously. This bolus will be repeated as needed to resolve Grade 2 and above symptoms at the discretion of assessing physician. Fluid maintenance will be continued using 0.45% NaCl, 5% dextrose, and 20 mEq KCL per liter at a rate of 100 mL/hour until subject is able to resume oral rehydration. If the subject develops grade 4 hypotension despite the aggressive fluid management, the subject will be transferred from the inpatient unit to a hospital setting.

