9.1.4. Unsolicited Adverse Events

An unsolicited AE is an AE that was not solicited using a Subject Diary and that was spontaneously communicated by a subject who has signed the informed consent or a solicited local or systemic AE that continues beyond the solicited period at day 7 after vaccination.

Potential unsolicited AEs may be medically attended (defined as symptoms or illnesses requiring hospitalization, or emergency room visit, or visit to/by a health care provider), or were of concern to the subjects. In case of such events, subjects will be instructed to contact the site as soon as possible to report the event(s). The detailed information about the reported unsolicited AEs will be collected by the qualified site personnel during the interview and will be documented in the subject's records.

205626 (S SONNEI MONO GMMA SBVGH-003 [H03_03TP]) Protocol Amendment 6 Final

Unsolicited AEs that are not medically attended nor perceived as a concern by subjects will be collected during interview with the subjects and by review of available medical records at the next visit

Unsolicited AEs will be collected until 28 days after each vaccination and until 28 days after challenge.

9.1.5. Clinical laboratory parameters and other abnormal assessments qualifying as adverse events or serious adverse events

In absence of diagnosis, abnormal laboratory findings (e.g., clinical chemistry, hematology, urinalysis) or other abnormal assessments that are judged by the investigator to be clinically significant will be recorded as AE or SAE if they meet the definition of an AE or SAE (refer to Sections 9.1.1 and 9.1.2). Clinically significant abnormal laboratory findings or other abnormal assessments that are present at baseline and significantly worsen following the start of the study will also be reported as AEs or SAEs.

The investigator will exercise his or her medical and scientific judgment in deciding whether an abnormal laboratory finding or other abnormal assessment is clinically significant. Clinically significant modifications in hematology will be assessed by medical judgment based on interpretation of deviations from institution's normal values and recommendations from CBER FDA GUIDANCE FOR INDUSTRY: Toxicity Grading Scale for Healthy Adults and Adolescent Volunteers Enrolled in Preventive Vaccine Clinical Trials and predefined list of sign and symptoms related to neutropenia.

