	3	>2 episodes within a 24-hour period and requires medical intervention	
	4	ER visit or hospitalization for hypotensive shock	
Diarrhea**	0	Absent	
1		2-3 Grade 3-5 stools (loose or watery) or <400 g/Grade 3-5 (loose or watery) stools per 24 hours	
	2	4-5 Grade 3-5 stools (loose or watery) or 400-800 g/ (loose or watery) Grade 3-5 stools per 24 hours	
	3	6 or more Grade 3-5 stools (loose or watery) or >800 g/Grade 3-5 (loose or watery) stools per 24 hours or requires medical intervention	
	4	\geq 10 loose stools (Grade 3 to 5) or \geq 1000 grams of Grade 3 to 5 stools within 24 hours	

[#]Same grading is used for events present both post-vaccination and post-challenge.

The maximum intensity of local injection-site erythema/induration/fever will be scored at GSK Biologicals as follows:

	Erythema/Induration
0:	< 25 mm
1:	≥ 25 - ≤ 50 mm
2:	> 50 - ≤ 100 mm
3:	> 100 mm

	Fe	ver	
Grade 0	Grade 1	Grade 2	Grade 3
Absent	Mild	Moderate	Severe
≤ 37.9°C	$\geq 38.0^{\circ}\text{C} - 38.9^{\circ}\text{C}$	$\geq 39.0^{\circ}\text{C} - 39.9^{\circ}\text{C}$	≥ 40.0°C

The investigator will assess the maximum intensity that occurred over the duration of the event for all unsolicited AEs (including SAEs) recorded during the study. The assessment will be based on the investigator's clinical judgment.

Every effort should be made by the investigator to evaluate safety information reported by a subject for an underlying diagnosis and to capture this diagnosis as the event in the AE page. In other words, the practice of reporting only symptoms (e.g., "cough" or "ear pain") are better reported according to the underlying cause (e.g., "asthma exacerbation" or "otitis media").

^{*}Fever is defined as temperature ≥ 38.0°C / 100.4°F. The preferred location for measuring temperature in this study will be the oral cavity.

^{**}The end of a diarrheal episode occurs when a volunteer does not pass any Grade 3-5 stool within 24 hours. ER: emergency room.

205626 (S SONNEI MONO GMMA SBVGH-003 [H03_03TP])
Protocol Amendment 6 Final

The severity of events reported on the Adverse Events eCRF will be determined by the investigator as:

Mild:	Transient with no limitation in normal daily activity
Moderate:	Some limitation in normal daily activity
Severe:	Unable to perform normal daily activity

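### Fatigue and chills can decide four secondary endpoints, but Sections 4.2 and 9.1.3.3 and Table 20 disagree on whether they are collected and graded after challenge

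*Protocol*

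**What the plan says.** Protocol Section 4.2 gives a symptom list for each use of dysentery. For the second shigellosis definition (any reportable symptom) and for more severe shigellosis (a severe symptom, or an oral temperature of at least 38.0°C), the list is "headache, fatigue, arthralgia, malaise, myalgia, chills, nausea, abdominal cramping, abdominal pain, gas, anorexia, vomiting". For the stand-alone dysentery endpoint and the confirmed-shedding composite, "constitutional/enteric symptoms consist of headache, fatigue, arthralgia, malaise, myalgia, chills, nausea, abdominal cramping, abdominal pain, gas, anorexia, vomiting, and fever". The list for the CHIM definition is shorter: "In this case constitutional/enteric symptom are the following: nausea, abdominal pain, abdominal cramping, myalgia, arthralgia, malaise".

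Section 9.1.3.3 describes what the investigator records from the day of challenge to Day 64: "These events include diarrhea, abdominal pain, abdominal cramps, gas, anorexia, nausea, headache, myalgia, malaise, arthralgia, fever, and vomiting". Fatigue and chills are not named.

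Table 20 in Section 9.3.3.2.1 gives the intensity scales. Fatigue carries the hash sign, which the footnote explains: "Same grading is used for events present both post-vaccination and post-challenge". Chills appears only among the post-vaccination events, without the hash sign, and has no row under the challenge heading.

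There are also general provisions. During the inpatient stay, Section 3.2 says "subjects will be monitored daily for AEs, gastrointestinal or other systemic signs and symptoms". Section 9.1.4 adds "Unsolicited AEs will be collected until 28 days after each vaccination and until 28 days after challenge". Section 9.3.3.2.1 has a general mild, moderate or severe scale for events entered on the adverse event form.

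**The concern.** A symptom that can decide whether a subject is a case should be asked for in the same way, on the same days and on a defined scale, for every challenged subject. Here the endpoint definition, the collection list and the grading table give different answers for two symptoms. Both are solicited after vaccination (Table 16), so the question and the scale already exist in the study.

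At stake is consistent case finding for secondary efficacy endpoints. Two of them, the second shigellosis definition and more severe shigellosis, were added under Amendment 5 to make results easier to compare with other challenge studies. A subject whose only qualifying symptom is fatigue or chills could be a case under Section 4.2 and yet have no matching record in the post-challenge symptom data.

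**Working it through.** The protocol states no figure on this point, so there is none to reproduce. The check is a comparison of lists, treating abdominal cramps and abdominal cramping as the same item.

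**Step 1. Endpoint list against collection list.**

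| Symptom in the Section 4.2 twelve-item list | Named in 9.1.3.3 | Post-challenge scale in Table 20 |
|---|---|---|
| Headache, arthralgia, malaise, myalgia | Yes | Yes (hash sign) |
| Nausea, abdominal cramping, abdominal pain, gas, anorexia, vomiting | Yes | Yes (own row) |
| Fatigue | No | Yes (hash sign) |
| Chills | No | No |

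So 4 + 6 = 10 of 12 symptoms agree across all three places, and 12 − 10 = 2 do not. For fatigue, Section 9.1.3.3 and Table 20 conflict. For chills, those two places agree with each other but not with Section 4.2.

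**Step 2. Definitions that are not touched.** All six CHIM dysentery symptoms are named in Section 9.1.3.3 (0 of 6 missing). The primary case definition in Section 4.3 uses shedding, moderate or severe diarrhea and an oral temperature of at least 38.5°C. It contains no constitutional symptom, so the 21-case sample size calculation in Section 11.4 is unaffected.

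**Step 3. When a dysentery case would be missed.** All of the following must hold:
- the subject has at least two loose stools with gross blood in 24 hours;
- fatigue or chills is the only qualifying symptom (for more severe shigellosis, the only severe one);
- fever does not qualify the subject, where fever counts;
- the symptom is not recorded separately, or not with a grade, through monitoring or adverse event reporting.

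**Step 4. How far the general provisions fill the gap.** Sections 3.2 and 9.1.4 allow either symptom to be recorded, and the general scale allows it to be called severe. Against that, Section 9.3.3.1 relies on a non-leading question and tells the investigator, where a diagnosis can be made, to enter it in place of its component signs and symptoms. Section 9.3.3.2.1 repeats the preference for the underlying cause. In a subject with shigellosis after challenge, fatigue or chills could properly be absorbed into that diagnosis, whereas the endpoint needs the symptom and its grade.

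**Step 5. Effect on efficacy.** Section 11.8 defines VE = 1 − RR, with RR = p_v / p_p (vaccine rate over placebo rate). If a fraction f of true cases is missed in each arm, the expected rates give RR = (1 − f)p_v / [(1 − f)p_p] = p_v / p_p. VE keeps its value and the interval widens because there are fewer cases. For scale, 36 × (1 − 0.22) = 28.08, about 28 evaluable subjects per arm, so one missed case moves an arm's observed rate by 1/28 = 3.6 percentage points. The document gives no value for f.

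**The case against.** The best defence is that little can be lost. Ten of the twelve symptoms are solicited, including malaise, which uses the same four-level scale as fatigue. Temperature of at least 38.0°C is an alternative route into more severe shigellosis. Subjects are on an inpatient unit and assessed daily. Table 20 is a table of solicited symptoms and treats fatigue as present after challenge, and the Section 9.1.3.3 list opens with a word that need not make it exhaustive. Severe chills can be graded on the general scale, whose top level is close in meaning to the chills scale used after vaccination. Section 11.11 makes comparisons without a success criterion descriptive.

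Most of this stands and limits the size of the point. It does not remove it. If the list is open, nothing fixes whether the two symptoms are asked about, and the fallback route favors a diagnosis over the symptom.

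A reader might infer more than the documents support:
- **That the endpoints are in fact under-ascertained.** This is only possible. No document shows that fatigue or chills occurs as the sole qualifying symptom, and the inpatient symptom form, which is not shown, may already ask about both.
- **That fatigue is simply not collected.** Table 20 says otherwise; the finding for fatigue is a contradiction.
- **That vaccine efficacy is biased.** Section 6.3 keeps evaluators unaware of allocation, so a difference in recording between arms is not to be expected.
- **That the diarrhea arm of more severe shigellosis is also exposed.** Section 4.3 requires a severe symptom there but gives no list, and Section 4.2 sets its list for dysentery only.

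**Conclusion.** The inconsistency is real and minor. Four secondary endpoints use two symptoms that the post-challenge list does not name, and one of these, chills, also lacks a symptom-specific post-challenge scale. Those endpoints may be under-ascertained. The number of missed cases cannot be derived from the protocol, and no shift in efficacy should be attached to it.

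The judgment that the cost is precision more than bias assumes that blinded, identical collection in both arms leads to similar losses in each. The primary endpoint, its success criterion, the sample size and the CHIM dysentery symptom list are not affected. The case for acting is that the gain in ascertainment is specific and costs almost nothing.

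**What to change.** Add fatigue and chills to the post-challenge events in Section 9.1.3.3, and give chills the hash sign in Table 20. Every symptom named in Section 4.2 is then asked for and graded on each inpatient day in both arms, and the three places agree. The cost is two more lines on the inpatient symptom form and a short wording change; subjects are already assessed daily on the unit. If the site's form already covers both symptoms, only the protocol wording needs to change.

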9.1.4. Unsolicited Adverse Events

An unsolicited AE is an AE that was not solicited using a Subject Diary and that was spontaneously communicated by a subject who has signed the informed consent or a solicited local or systemic AE that continues beyond the solicited period at day 7 after vaccination.

Potential unsolicited AEs may be medically attended (defined as symptoms or illnesses requiring hospitalization, or emergency room visit, or visit to/by a health care provider), or were of concern to the subjects. In case of such events, subjects will be instructed to contact the site as soon as possible to report the event(s). The detailed information about the reported unsolicited AEs will be collected by the qualified site personnel during the interview and will be documented in the subject's records.

205626 (S SONNEI MONO GMMA SBVGH-003 [H03_03TP]) Protocol Amendment 6 Final

Unsolicited AEs that are not medically attended nor perceived as a concern by subjects will be collected during interview with the subjects and by review of available medical records at the next visit

Unsolicited AEs will be collected until 28 days after each vaccination and until 28 days after challenge.

9.1.5. Clinical laboratory parameters and other abnormal assessments qualifying as adverse events or serious adverse events

In absence of diagnosis, abnormal laboratory findings (e.g., clinical chemistry, hematology, urinalysis) or other abnormal assessments that are judged by the investigator to be clinically significant will be recorded as AE or SAE if they meet the definition of an AE or SAE (refer to Sections 9.1.1 and 9.1.2). Clinically significant abnormal laboratory findings or other abnormal assessments that are present at baseline and significantly worsen following the start of the study will also be reported as AEs or SAEs.

The investigator will exercise his or her medical and scientific judgment in deciding whether an abnormal laboratory finding or other abnormal assessment is clinically significant. Clinically significant modifications in hematology will be assessed by medical judgment based on interpretation of deviations from institution's normal values and recommendations from CBER FDA GUIDANCE FOR INDUSTRY: Toxicity Grading Scale for Healthy Adults and Adolescent Volunteers Enrolled in Preventive Vaccine Clinical Trials and predefined list of sign and symptoms related to neutropenia.

